### **8.9.1. Concentration Values Below the Limit of Quantitation**

Plasma concentrations below the limit of quantitation will be set to one-half of the lower limit of quantitation for the calculation of descriptive statistics of unadjusted plasma nicotine concentrations and for the calculation of baseline-adjusted nicotine concentrations.

### **8.9.2. Elevated Baseline**

Upon review of the bioanalytical data, subjects with baseline nicotine levels that are higher than their 120-minute values will be considered as not meeting the pre-exposure smoking abstinence criteria and will be considered for exclusion from the PK Subpopulation. Subjects who do not meet the abstinence criteria in  $\geq 50\%$  of their visits will be excluded from the PK Subpopulation.

### **8.9.3. Baseline-Adjusted Nicotine Concentration**

Individual nicotine concentrations will be adjusted for baseline nicotine (“baseline-adjusted”) and all PK parameters will be calculated based on the adjusted concentrations. Baseline adjustment will be performed by subtraction of the baseline nicotine concentration from each nicotine concentration obtained after test product use on that day for each subject.

## **8.10. SAFETY ANALYSES**

### **8.10.1. Mass Change (Product Use)**

The blu disposable e-cigarette weight difference of before and after use in both use sessions will be summarized descriptively.

The amount of liquid consumed in the controlled product use session will not be combined with the amount consumed in the *ad libitum* session.

### **8.10.2. Adverse Events**

An AE is any untoward medical occurrence associated with the use of the study product, whether or not considered study product-related. An AE can therefore be any unfavorable and unintended sign (including an abnormal laboratory finding), symptom, or disease temporally associated with the use of a study product, whether or not related to the study product.

Adverse events will be coded using the Medical Dictionary for Regulatory Activities (MedDRA) coding dictionary version 22 or higher.

AEs will be reported under the product last used when the onset of AE occurred or when the severity of an existing AE changes.

Statistical Analysis Plan  
Protocol No.: Fontem-PK-01

The following AE summaries will be presented.

- Overall Summary of AEs: the number of events, number and percent of subjects who experienced AEs, SAEs, severe AEs, related AEs, and AEs leading to study discontinuation; summarized by study product and overall.
- Incidence of AEs by MedDRA SOC and PT: AEs will be summarized by SOC and PT. If a subject has more than one occurrence of the same PT, then the PT will be counted only once for that subject under the SOC in which it was categorized.
- Incidence of AEs by PT and maximum severity will be presented for each level of severity by PT and product use. When a subject experiences the same AE (PT) at more than one level of severity, only the most severe one will be counted.

Additionally, listing of AEs will be presented including all data collected in the CRF, along with the derived variable, duration of AE, and the coded variables, SOC and PT.

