Safety Data	On-study safety evaluations will include measurement of heart rate and blood pressure at the start, during, and at the end of each study site visit, temperature checks before each study site visit, and pregnancy tests in female subjects at the start of each product use visit. AEs reported by the subjects or observed by study personnel will be monitored from the time a subject uses the first investigational product/own brand cigarette (Visit 2) until the end of the study and will be reported by subjects at the follow-up. Any concomitant medications taken in the 30 days prior to Visit 1 through follow-up will also be recorded.
Bioanalysis	Nicotine analysis will be performed at an appropriate analytical laboratory using validated methods.
Statistics	Since this study is the first to examine the nicotine PK in subjects using these blu disposable e-cigarettes, no formal power calculations will be performed. A summary of statistical analysis plans follows. Analysis of Nicotine Pharmacokinetics: Pharmacokinetic parameters of plasma nicotine levels will be calculated using non-compartmental methods. Plasma concentrations and the computed plasma PK parameters will be listed for each study product and subject. Plasma nicotine levels will be plotted as mean concentration in relation to time, with 95% confidence intervals of the mean for each product at each time point. The following PK parameters will be calculated; all parameters will be baseline adjusted using the value at time -5 minutes: 
 • $C_{max,0-120}$ = Maximum plasma concentration during defined use session • $T_{max,0-120}$ = Time of maximum plasma concentration during defined use session • AUC_{0-120} = Area under the plasma concentration-time curve from time 0 to 120 minutes during defined use session • $C_{avg,0-120}$ = Average concentration from 0 to 120 minutes defined as $AUC_{0-120}/120$ minutes.

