9.13 Trial of Study Products

At Screening, potential subjects will participate in a brief, observed trial use of a blu disposable e-cigarette to demonstrate that they can successfully comply with the instructions for use of study products using the following protocol:

- Study staff will instruct the subject on the proper use of the ENDS device.
- Subject will take up to 5 *ad lib* puffs from Study Product C (Table 1) to become familiar with the product and demonstrate that they can inhale the aerosol without excessive coughing or discomfort.
- Based on the testing, subject expresses confidence in his/her ability to use each of the study products during the at-home familiarization period as well as the puffing sessions during Visits 3 to 7.

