9.15.1 Adverse Events

An AE is any untoward medical occurrence associated with the use of the study product, whether or not considered study product-related. An AE can therefore be any unfavorable and unintended sign (including an abnormal laboratory finding), symptom, or disease temporally associated with the use of a study product, whether or not related to the study product.

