9.15.1.2 Reporting

All AEs occurring during this clinical trial after the subject has used the first study product will be recorded on the CRF, including the date and time of onset, action taken, outcome (resolved, improved, unchanged, worse, fatal, or unknown/lost to follow-up), duration, relationship to product use, and severity for each event.

Events captured between Screening and the first study product use will be documented as baseline signs and symptoms.

The investigator will review each event and assess its relationship to product use as unrelated, unlikely, possibly, probably, or likely.

In addition, each sign or symptom reported will be graded on a 3-point severity scale using mild, moderate, or severe.

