10.3.5 Safety

All clinical safety data will be summarized by subject and time point as appropriate.

All AEs captured in the database will be listed in by-subject data listings. However, only study product use-emergent AEs will be summarized. A study product use-emergent AE is defined as an AE that is starting or worsening at the time of or after the first study product use.

Frequencies of subjects with study product use-emergent AEs, regardless of relationship to study product, will be summarized and sorted by system organ class. Frequencies of subjects with study product use-emergent serious AEs will be likewise summarized. Frequencies of study product use-emergent AEs will be summarized by severity and relationship to study product.

All concomitant medications recorded will be listed by subject.

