### **8.4. MEDICAL HISTORY**

Abnormalities identified from any physical examinations at the Screening visit, if required by the study physician, will be recorded in the CRF as Medical History. Any medical conditions with a start time prior to first use of study product will be recorded as part of the subject's medical history.

Medical history data will be coded with MedDRA Version 22.0 or later and will be listed by System Organ Class (SOC) and Preferred Term (PT).

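### AE collection is placed at Visit 2 although Product C is first used at Visit 1, and the last-used rule cannot be applied reliably to AEs that start off-site

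*SAP*

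**What the plan says.** **Start of AE collection.** The Safety Data entry of the Protocol Synopsis has AEs "monitored from the time a subject uses the first investigational product/own brand cigarette (Visit 2"). The flow charts in the Protocol and in SAP Appendix 1 mark the AE row for Visits 2 to 7 and follow-up, not for Screening. Three other sections tie the start to a first product use without naming a visit:

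- Protocol 9.15.1.2: "Events captured between Screening and the first study product use will be documented as baseline signs and symptoms".
- Protocol 10.3.5 defines a use-emergent AE as one "starting or worsening at the time of or after the first study product use".
- SAP 8.4, on medical history: "Any medical conditions with a start time prior to first use of study product will be recorded".

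**First contact with a study product.** Protocol 9.13 has potential subjects at Screening take up to 5 "puffs from Study Product C (Table 1) to become familiar with the product". The session also serves as a tolerability check, in which each of them has to "demonstrate that they can inhale the aerosol without excessive coughing or discomfort". Product C is one of the five e-cigarettes in Table 1. Protocol 9.15.1 (repeated in SAP 8.10.2) counts as an AE any sign, "symptom, or disease temporally associated with the use of a study product, whether or not related to the study product".

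**Attribution.** SAP 8.10.2 states that "AEs will be reported under the product last used when the onset of AE occurred", and applies the same rule when the severity of an existing AE changes. AEs are then summarized by study product and overall. Protocol 4.3.4 gives subjects the next e-cigarette for home use on the day before each of Visits 3 to 7 and lets them smoke their own brand (Product F) as well, outside the 12-hour abstinence. Protocol 7.3 has staff document start and stop times of use episodes and keep dispensing records. Neither document describes recording when products are used at home.

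**The concern.** The first study product a subject inhales is Product C at Visit 1, but the passages that name a visit open AE collection at Visit 2. On that reading, coughing or nausea after the Visit 1 puffs meets the protocol's own AE definition and is still filed as a baseline sign or as medical history. A subject screened out because of such a reaction is also outside the Safety Population, which requires completed eligibility (Protocol 10.2.1, SAP 5.1).

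The attribution rule needs to know which product was used last before onset. In the clinic that is known. At home it is not: on a familiarization day the subject may alternate between the new e-cigarette and own cigarettes. Between visits the last product used will often be F, whatever was tested in the clinic. Two analysts could apply the rule in good faith and fill different columns.

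At stake are the completeness of Product C safety reporting and the by-product AE tables. Overall safety of the e-cigarettes is a secondary objective, and the results are intended to support a PMTA.

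**Working it through.** The plan gives no figure on AE attribution and no AE rate, so there is none to reproduce. The counts below are days, puffs and subjects, not AEs.

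**1. Start point, passages side by side.**

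- Visit 2 reading: the Synopsis and both flow charts say so directly. Protocol 9.15.1.2 supports it by providing for events between Screening and first use, as though these were separate occasions.
- Visit 1 reading: taken alone, Protocol 9.15.1.2 and 10.3.5 (and SAP 8.4) speak only of first study product use, and Product C is a study product.
- No passage reconciles the two.

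**2. Who is exposed at Visit 1.** Protocol 5.2 plans 20 subjects plus 2 qualified alternates, so at least 20 + 2 = 22 people, plus an unstated number of screen failures. Exposure is up to 5 puffs, against 10 in the defined session (Protocol 9.14.1): 5/10 = up to 50% of that puff count. Visit 2 follows 2 to 14 days later (Protocol 8.2).

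**3. Attribution on familiarization days.** Assume 20 completers. Planned familiarization days: 20 × 5 = 100.

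| Reading of the rule | Column for a familiarization-day AE |
|---|---|
| Literal (actual last use) | New e-cigarette or F; not determinable from any planned record |
| In-clinic times only (an assumption) | Previous visit's product |

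On the in-clinic assumption the day before Visit 3 goes to F: 20 × 1 = 20 days (20%). The days before Visits 4 to 7 go to a different e-cigarette: 20 × 4 = 80 days (80%). None goes to the product being familiarized. With 4 subjects per row of a 5 × 5 Latin square (also an assumption), each e-cigarette has 20 familiarization days, of which 4 would be credited to F and 16 to other e-cigarettes.

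**4. Share of the time between visits.** Visits are at least 2 days apart, so Visit 2 to Visit 7 spans at least 5 × 2 = 10 days and familiarization days are at most 5/10 = 50%. If the approximate 3 weeks in the Synopsis is 21 days and includes the 5 to 7 days to follow-up (assumption), the span is 14 to 16 days and the share is 5/16 = 0.31 to 5/14 = 0.36.

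**5. Effect of one subject.** Moving one subject changes a 20-subject column by 1/20 = 5.0 percentage points, and only if that subject has no other qualifying AE in the column.

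**6. Can dates alone define product windows?** The familiarization day is the next visit date minus 1, which is at least the previous visit date + 2 − 1 = previous visit date + 1. It therefore never falls on the previous visit day. All 5 boundaries per subject (100 of 100 for 20 subjects) are fixed without home-use times.

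**The case against.** Several points on the other side stand.

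- A reader might infer that the plan books familiarization-day AEs to the previous product. The documents do not support that. SAP 8.10.2 does not say last used in the clinic, and nothing makes the staff-recorded times the source for attribution. Staff ask about AEs before each product use and record onset date and time (Protocol 9.15.1.1 and 9.15.1.2), so last use could be asked about. The CRF is not among the documents. The 20 and 80 days follow only from the in-clinic assumption.
- A reader might also infer that Visit 1 reactions go unrecorded. They do not support that either. Non-serious events are relabelled as baseline signs or medical history, not discarded. Protocol 9.15.1.3 sets no Visit 2 start for SAEs, so a serious Visit 1 reaction is arguably already reportable.
- The impact is limited. The safety objective concerns the e-cigarettes overall. Even on the in-clinic reading, 80 of the 100 days move between e-cigarettes of the same 2.4% strength and leave the pooled e-cigarette count unchanged. The tables are descriptive, and the listings allow review of individual events.

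These points limit the size of the problem but do not remove it. The sections on first use still conflict. Asking about last use is possible but not prescribed, and neither reading of the attribution rule reliably credits the familiarization product. Listings do not correct by-product counts.

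**Conclusion.** Both points hold, as ambiguities in the plan with a minor-to-moderate effect.

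1. **Start point.** The Synopsis and flow charts place the start of AE collection at Visit 2, after a study product has already been used. On that reading, non-serious Product C reactions at Visit 1 do not enter AE reporting although they meet the AE definition. At least 22 qualified subjects and all screen failures who take the trial puffs are concerned.
2. **Attribution.** The last-used rule cannot be applied reliably to off-site onsets. The literal reading lacks the data it needs; the in-clinic reading, if adopted, credits 0 of 100 familiarization days to the product being familiarized.

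AEs with onset in the use sessions and overall AE counts from Visit 2 on are unaffected. It would go too far to say that the safety results are distorted: no AE rate is given, so no number of misplaced AEs can be derived. The counts assume 20 completers.

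**What to change.** **Start point.** Reconcile the Synopsis, both flow charts, Protocol 9.15.1.2 and 10.3.5, and SAP 8.4 so that AEs and SAEs are recorded from the first puff of Product C at Visit 1. Report events from then until first use at Visit 2, including those in screen failures, in a separate Product C trial-use listing with a count.

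**Attribution.** In SAP 8.10.2, replace the last-used rule with a date-based one, applied in the same way to every product and to both onset and change in severity:

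- An event dated from an e-cigarette's familiarization day (for F, from first use at Visit 2) through the end of that product's visit day is counted under that product.
- All later off-site events, whether between visits or after Visit 7, go in one separate off-site column.
- Own-cigarette use before onset is flagged where reported.

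Dispensing records and visit dates suffice. The windows are two calendar days for each e-cigarette and one for F, which has no familiarization day; the table should say so. With visits at the 2-day minimum, no between-visit days fall in the off-site column. After Visit 7 it holds 20 × 5 = 100 to 20 × 7 = 140 subject-days before the follow-up call.

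**Cost.** SAP wording, a short protocol and flow-chart amendment, and a few AE records at screening. The rule follows the planned day of use, not confirmed use. A few AEs due to own cigarettes on a familiarization day will fall under an e-cigarette, and delayed events move to the off-site column. Onset times in the listings make both visible.

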Inclusion/ Exclusion Criteria	
The key inclusion criteria are:
 
 Subjects must be current smokers (≥ 10 per day) of factory-made combustible cigarettes (eCO >10 ppm at screening) for at least 6 continuous months before Visit 1 and may be occasional users of e-cigarettes. Subjects have urine cotinine >200 ng/mL at Screening 
The key exclusion criteria are:
 
 Subjects who, in the judgment of the study physician, have recent or active COVID 19 infection, based on results from COVID-19 screening, body temperature $\geq 100.4^{\circ}\text{F}$, and/or laboratory test results suggestive of recent exposure to SARS-CoV-2. Subjects who have an acute illness (e.g., upper respiratory tract infection, viral infection) requiring treatment in the 4 weeks prior to Visit 1. Subjects with significant abnormalities in their clinical laboratory evaluations or electrocardiogram. Subjects who have used any nicotine or tobacco product other than e-cigarettes or factory-made combustible cigarettes in the 14 days prior to Visit 1. Subjects who are self-reported or observed (during the trial session at Visit 1) non-inhalers during ENDS/cigarette use. Subjects who have used any prescription or over-the-counter smoking cessation treatments, including, but not limited to any form of nicotine replacement therapy (NRT), varenicline, or bupropion within 30 days prior to Visit 1. 																							

	
 • Subject has a history or diagnosis of adult asthma, COPD (including emphysema and chronic bronchitis), or use of an inhaler within the past 3 months. • Subject has an active respiratory infection at time of the Screening Visit.
Duration of Study	Screening duration: approximately 14 days. Study duration: approximately 3 weeks.
Blood Sampling	Total blood draw volume is expected to be 510 mL for each subject during the study.
Post-Study Tests	A post-study follow-up will be performed with all subjects 5 to 7 days after their last study site visit, which will be conducted via a telephone call with the subjects. A full physical examination and safety assessments will be conducted only if indicated after review by the study physician.

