7. STUDY PRODUCTS/MATERIALS

7.1 Description of Study Products

All blu disposable e-cigarettes (Table 1) will be provided by the sponsor.

Table 1: Study Products

Product	Flavor	Nicotine Strength
A		2.4%
B		2.4%
C		2.4%
D		2.4%
E		2.4%
F	Subject's Usual Brand Combustible Cigarette	

blu disposable e-cigarettes are intended for one-time use only and cannot be disassembled. Disposables contain an internal tank pre-filled with e-liquid and include an internal battery that is not rechargeable. Upon taking a draw on the disposable, a sensor activates the battery to generate heat. Once heated, e-liquid is converted to vapor. Instructions provided to subjects will include: 1. Remove the rubber cap from the mouthpiece at the end of the disposable. 2. As you inhale, the blue LED tip on the end of the disposable will illuminate.

At Visit 2, subjects will smoke their own brand of combustible cigarette.

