8.2 Visits 2 to 7 (Combustible Cigarette Smoking and ENDS Use)

Visit 2 will occur between 2 and 14 days after Visit 1.

Visits 2 to 7 will be scheduled before 1 pm, and each of these visits will last approximately 3.5 hours. Visits 2 to 7 will occur at least 2 days following the previous visit.

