8.3 Post-study Assessments

Between 5 and 7 days after the last study site visit (Visit 7), a post-study follow-up will be performed, which will be conducted via a telephone call with the subjects. A full physical examination and safety assessments will be conducted only if indicated after review by the study physician.

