## **4. RANDOMIZATION AND BLINDING**

### **4.1. RANDOMIZATION**

Eligible subjects at Visit 2 will be assigned a randomization number beginning with 2001. The randomization will determine the order in which the subjects will test the study products at Visits 3 to 7. The randomization code for the study products will be produced using a computer-generated Latin-square procedure.

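### By-product AE percentages in SAP 8.10.2 rest on observation windows that differ systematically between the cigarette and the e-cigarettes, and the SAP does not fix which product owns the time between visits

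*SAP*

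**What the plan says.** SAP 8.10.2 gives the attribution rule: "AEs will be reported under the product last used when the onset of AE occurred", or when the severity of an existing event changes. The overall AE table gives numbers of events and numbers and percentages of subjects, "summarized by study product and overall". The section sets no end to a product's window and makes no adjustment for time observed.

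The timing comes from the protocol:

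- The Synopsis (Safety Data) has AEs monitored from first product use at Visit 2 "until the end of the study and will be reported by subjects at the follow-up".
- Section 7.1 fixes the cigarette's place: "At Visit 2, subjects will smoke their own brand of combustible cigarette". Only the five e-cigarettes are ordered at random over Visits 3 to 7. SAP 4.1 says the "randomization code for the study products will be produced using a computer-generated Latin-square procedure".
- Section 8.2: "Visits 2 to 7 will occur at least 2 days following the previous visit". No maximum is given.
- Section 8.3: "Between 5 and 7 days after the last study site visit (Visit 7), a post-study follow-up will be performed".
- The Synopsis (Duration of Study): "Study duration: approximately 3 weeks".
- Section 4.3.4 adds one day of home use of the next e-cigarette before each of Visits 3 to 7, with usual-brand smoking still allowed. Apart from that, section 4.3.2 bars nicotine only for the 12 hours before a visit.

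SAP Table 1 lists the subject's usual brand as product F. Neither document says whether smoking it at home makes it the product last used.

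**The concern.** Under an open-ended rule, each product collects AEs until another product takes over. The Visit 7 product has no successor, so it collects them until the follow-up call. The Latin square shares that final period among A to E, but it cannot share it with a cigarette fixed at Visit 2. Background events such as colds or headaches would then be counted over different lengths of time in different columns, with no product effect at all.

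The stake is interpretation. SAP 3.1 says the results are meant to support a regulatory application that sets the e-cigarettes against the usual brand, so readers will compare the A to E columns with F. Events during the roughly 3-hour site session are not affected. The issue is events with onset afterwards.

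**Working it through.** The plan states no AE rate or window length, so there is no figure of its own to reproduce. Let g be the gap between visits in days and f the follow-up after Visit 7 (5 to 7 days, Protocol 8.3).

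**Gap.** The minimum is 2 days (Protocol 8.2). If 3 weeks runs from Visit 2 to a call 6 days after Visit 7, g = (21 - 6)/5 = 3. If it covers Visits 2 to 7 only, g = 21/5 = 4.2.

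**Share of the final period.** With 20 subjects and 5 e-cigarettes in a balanced square, each e-cigarette is at Visit 7 in 20/5 = 4 subjects.

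**Only scheduled site use counts.** Cigarette window = g. Mean e-cigarette window = (4g + f)/5. Ratio = (4g + f)/(5g).

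| g | f = 5 | f = 6 | f = 7 |
|---|---|---|---|
| 2 | 1.30 | 1.40 | 1.50 |
| 3 | 1.13 | 1.20 | 1.27 |
| 4.2 | 1.04 | 1.09 | 1.13 |
| 5 | 1.00 | 1.04 | 1.08 |
| 6 | 0.97 | 1.00 | 1.03 |
| 7 | 0.94 | 0.97 | 1.00 |

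If the 21 days include a 7-day follow-up, g = (21 - 7)/5 = 2.8 and the ratio is (11.2 + 7)/14 = 1.30.

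**Familiarization use also counts.** The switch comes one day before the visit. Cigarette window = g - 1. Mean e-cigarette window = (4g + f + 1)/5. For f = 5 to 7 the ratio is 2.80-3.20 at g = 2, 1.80-2.00 at g = 3 and 1.43-1.55 at g = 4.2. For example, at g = 3 and f = 6, (12 + 6 + 1)/5 = 3.8 days against 2.

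**Home usual-brand smoking counts as product F.** Assume smoking resumes 1 to 12 hours after a 3.5-hour visit, and that familiarization adds 0 to 1 day. Each e-cigarette window is then (1 + 3.5)/24 = 0.19 days to (12 + 3.5)/24 + 1 = 1.65 days. Product F takes the rest of 5g + 6 days. At g = 2 with the longest e-cigarette window, F has 16 - 5 × 1.65 = about 7.8 days, a ratio of 0.21. At g = 4.2 with the shortest, F has 27 - 5 × 0.19 = about 26 days, a ratio of 0.01.

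**Effect on percentages, site-only attribution, no product effect.** Assume 0.05 AEs per subject-day, so incidence over t days is 1 - exp(-0.05t). With f = 6, the Visit 7 product has 1 - exp(-0.30) = 25.9%.

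- g = 2: cigarette 9.5%; e-cigarette (4 × 9.5 + 25.9)/5 = 12.8%. Excess 3.3 points, or 0.7 of a subject in 20.
- g = 3: 13.9% against 16.3%. Excess 2.4 points, or 0.5 of a subject.
- g = 4.2: 18.9% against 20.3%. Excess 1.4 points, or 0.3 of a subject.

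The rate is an assumption, so a range is needed. At g = 2 and f = 6, a 2-day risk of 5% gives 1.0 against 1.4 subjects in 20, 10% gives 2.0 against 2.7, and 20% gives 4.0 against 5.2. Only the last exceeds one subject. At g = 3, the 20% case gives 5.7 against 6.5.

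**The case against.** The strongest case on the other side has five parts.

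- **Direction.** A reader might infer that e-cigarette AE incidence is inflated against the cigarette. The documents do not support that without qualification. It follows if only site use, or site and familiarization use, counts. If product F includes home smoking, most AEs between visits and after Visit 7 fall to the cigarette. That reading would be hard to apply event by event: Protocol 7.3 has staff record times of product-use episodes, but neither document provides for timing home cigarettes. The ambiguity is still the plan's, and it stands.
- **Gap.** Protocol 8.2 has no maximum, and under site-only attribution the contrast disappears at gaps of 5 to 7 days. True, but five such gaps take 25 to 35 days from Visit 2 to Visit 7, which fits poorly with about 3 weeks. The 2-day minimum fits only loosely too: 5 × 2 plus 5 to 7 days is 15 to 17 days.
- **Visit 7 contrast.** It is tempting to quote the Visit 7 window as 2.5 to 3.5 times the cigarette's at a 2-day gap. That applies to 4 of 20 subjects per e-cigarette, and the averaged ratios above are the relevant ones.
- **Role of the table.** The AE table is not the only safety information by product. Heart rate and blood pressure are safety endpoints taken at the same times at every product visit (Protocol 9.12). The safety objective (SAP 3.2.2) names no cigarette comparison, and no AE test is planned. This limits the consequence to interpretation and leaves the unequal windows in place.
- **Existing data.** Onset date and time and relationship to product use are recorded for each AE, and all AE data are listed. A careful reader could rebuild the windows, but the planned tables do not.

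**Conclusion.** The point holds as a structural imbalance in window length, modest in size and uncertain in direction until the attribution rule is defined. Under site-only attribution, mean e-cigarette windows are 4-27% longer than the cigarette's at gaps of 3 to 4.2 days, up to 50% longer at 2 days, and about equal at 5 to 7 days. The other two readings move the ratio to about 1.4-3.2 (at gaps of 2 to 4.2 days) or to 0.01-0.21. At gaps consistent with the stated duration, no reading gives equal windows.

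The expected distortion under site-only attribution is below one subject in 20 per e-cigarette at 0.05 AEs per subject-day. It rests on assumed values for the actual gap, the AE rate and full completion of the visits. It does not affect any error rate. It is worth correcting because it falls on all five e-cigarette columns in the same direction, randomization cannot remove it, and the correction is cheap.

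**What to change.** In SAP 8.10.2:

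1. State that attribution follows scheduled study product use, so that usual-brand smoking at home does not move an event to product F.
2. Keep the product-last-used tables and add a by-product AE summary limited to onset within one identical window for every product. Start it at first puff at the site visit and end it before familiarization with the next product can begin, for example through the end of the visit day. Because visits only have to be scheduled before 1 pm, a fixed number of hours ending within that day would make the windows exactly equal.
3. Show familiarization-day AEs separately, under the e-cigarette dispensed.
4. Show AEs from the follow-up after Visit 7 separately, with days since last site use.

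The new summary should not replace the existing tables. That would drop familiarization-day e-cigarette events from every product column, and at a 2-day gap a 24-hour window could overlap the next product's familiarization day.

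The cost is SAP wording, one extra table and one derived flag. AE onset times (Protocol 9.15.1.2) and product-use start times (Protocol 7.3) are already recorded. The drawback is that the common-window table will hold fewer events.
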